9.7.2 DIEPSS, AIMS, and Barnes Akathisia Rating Scale (BARS)

For DIEPSS total score (total of scores for items 1 through 8) and score for each DIEPSS item, AIMS total score (total of scores for items 1 through 7) and score for each of the items 8 through 10, and BARS, descriptive statistics of actual measurements and changes from baseline at each time point and the last assessment time point and the worst

postdose measurement and its change from baseline will be calculated for each treatment group and for the overall brexpiprazole group.

In addition, analysis will be performed by the ANCOVA model with treatment group as a factor and baseline as a covariate. Least square means of each treatment group and differences in least square means between each brexpiprazole group and the placebo group, as well as the two-sided 95% CIs will be determined.

For DIEPSS total score (total of scores for items 1 through 8) and score for each DIEPSS item, AIMS total score (total of scores for items 1 through 7) and score for each of the items 8 through 10, and BARS in the antidepressant-responder treatment-continuation period (Phase A+), descriptive statistics of actual measurements and changes from baseline (before the start of the antidepressant-responder treatment-continuation period [Phase A+]) at each time point and the last assessment time point will be calculated overall and for each requisite concomitant medication in the Phase A+ set.

9.7.3 Columbia-Suicide Severity Rating Scale (C-SSRS)

Numbers and proportions of subjects for each C-SSRS item (suicidality, suicidal ideation, suicidal behavior, completed suicide, emergence of suicidal ideation, emergence of serious suicidal ideation, worsening of suicidal ideation, and emergence of suicidal behavior) at each time point and in the overall period after initiation of IMP treatment in the double-blind period (including the post-treatment observation period, at discontinuation, and unscheduled visits) will be determined for each treatment group and for the overall brexpiprazole group. A listing of subjects with emergence of suicidal ideation, emergence of serious suicidal ideation, worsening of suicidal ideation, and emergence of suicidal behavior will be provided. Items of suicidal ideation and suicidal behavior will also be summarized in the same manner.

- Suicidality: “Yes” for any item of suicidal ideation or suicidal behavior
- Suicidal ideation: “Yes” for any item of suicidal ideation
- Suicidal behavior: “Yes” for any item of suicidal behavior
- Emergence of suicidal ideation: Change from “No” at baseline to “Yes” after baseline for suicidal ideation
- Emergence of serious suicidal ideation: Change from “No” at baseline to “Yes” with Grade 4 or 5 after baseline for suicidal ideation
- Worsening of suicidal ideation: Increase in the grade of suicidal ideation from baseline
- Emergence of suicidal behavior: Change from “No” at baseline to “Yes” after baseline for suicidal behavior

Items of suicidal ideation and suicidal behavior in the antidepressant treatment period (Phase A) will also be summarized in the ADT set.

Items of suicidal ideation and suicidal behavior in the antidepressant-responder treatment-continuation period (Phase A+) will also be summarized in the Phase A+ set.

10 Pharmacokinetic Analyses

Pharmacokinetic analysis will be performed on the pharmacokinetic analysis set.

Descriptive statistics of plasma brexpiprazole concentrations at time points (0-6, 6-12, 12-18, 18-24, 24-30, and > 30 hours) after the most recent dosing as well as trough brexpiprazole concentrations (20-28 hours after the most recent dosing) and plasma brexpiprazole concentrations at all time points will be calculated by treatment group. The descriptive statistics will also be calculated by CYP2D6 phenotype (EM, IM, PM, and Unknown) in each treatment group and by requisite concomitant medication in each treatment group in the same manner.

The mean plasma brexpiprazole concentration over time and individual values at each time point after the most recent dosing will be plotted by treatment group. Plotted diagrams by CYP2D6 phenotype in each treatment group and by requisite concomitant medication in each treatment group will also be provided in the same manner.

Scatter plots of plasma brexpiprazole concentrations over time will be provided by treatment group. Scatter plots by CYP2D6 phenotype in each treatment group and by requisite concomitant medication in each treatment group will also be provided in the same manner.

Plasma brexpiprazole concentrations below the lower limit of quantitation will be handled as 0 (ng/mL) when their descriptive statistics are calculated and when plotted diagrams and scatter plots are created.

11 Pharmacodynamic Analyses

Not applicable.

12 Pharmacogenomic Analyses

CYP2D6 genotype (phenotype) will be tabulated as specified in [Section 7.2 Demographic and Baseline Characteristics](#). CYP2D6 phenotype will also be summarized in subgroup efficacy and safety analyses.

13 Interim Analysis

No interim analyses are planned.

14 Changes in the Planned Analyses

- The following changes were made to categorical analyses of QTc:
Only subjects with postdose QTc meeting the criteria will be summarized, instead of summarization at all time points.

Only subjects with QTc not meeting the criteria at baseline and meeting the criteria after baseline will be summarized.
- It has been decided that CYP2D6 phenotype will be tabulated as specified in [Section 7.2 Demographic and Baseline Characteristics](#). CYP2D6 phenotype will also be summarized in subgroup efficacy and safety analyses.
- The original plan of using the LOCF dataset in ANCOVA of safety endpoints was changed as follows: Measurements at each time point and at the last assessment time point and, as necessary, the worst postdose measurement will be included in the analysis.
- The original plan of calculating descriptive statistics of plasma brexpiprazole concentrations by treatment group in pharmacokinetic analysis was changed as follows: Descriptive statistics of plasma brexpiprazole concentrations at each time point after the most recent dosing, trough concentrations, and plasma drug concentrations at all time points will be calculated by treatment group, by CYP2D6 phenotype in each treatment group, and by requisite concomitant medication in each treatment group.

15 References

Not applicable.

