3.7.1.9 Acceptable Window for Testing

Observations/examinations and other procedures are to be performed within an acceptable window for testing, as specified in Table 3.7.1.9-1, with consideration of the availability of each subject for site visits, etc.

 Table 3.7.1.9-1
 Acceptable Window for Examinations/Assessment Period

The starting point of the antidepressant treatment period (Phase A) is the day of assessment at the initiation of the antidepressant treatment period (Phase A).

| Examination Point | Reference Day | Acceptable Window (From the Reference Day) |
|--|--|--|
| At screening | Day of assessment at the initiation of the antidepressant treatment period (Phase A) | Day -28 to -1 |
| Day of assessment at the initiation of the antidepressant treatment period (Phase A) | Day 1 | _ |
| Week 1 of the antidepressant treatment period (Phase A) | Day 8 | ± 2 days |
| Week 2 of the antidepressant treatment period (Phase A) | Day 15 | ± 2 days |
| Week 3 of the antidepressant treatment period (Phase A) | Day 22 | ± 2 days |
| Week 4 of the antidepressant treatment period (Phase A) | Day 29 | ± 2 days |
| Week 6 of the antidepressant treatment period (Phase A) | Day 43 | ± 2 days |
| Week 8 of the antidepressant treatment period (Phase A) | Day 57 | ± 2 days |
| At discontinuation | _ | _ |

At discontinuation: Performed within a possible window at a feasible time point.

 Table 3.7.1.9-1
 Acceptable Window for Examinations/Assessment Period

The starting point of the double-blind period (Phase B) is the day of assessment at Week 8 of the antidepressant treatment period (Phase A).

| Examination Point | Reference Day | Acceptable Window (From the Reference Day) |
|---|---------------|--|
| Day of assessment at Week 8 of the antidepressant | Day 1 | _ |
| treatment period (Phase A) | | |
| Week 1 of the double-blind period (Phase B) | Day 8 | $\pm 1 \text{ day}$ |
| Week 2 of the double-blind period (Phase B) | Day 15 | ± 2 days |
| Week 3 of the double-blind period (Phase B) | Day 22 | ± 2 days |
| Week 4 of the double-blind period (Phase B) | Day 29 | ± 2 days |
| Week 5 of the double-blind period (Phase B) | Day 36 | ± 2 days |
| Week 6 of the double-blind period (Phase B) | Day 43 | ± 2 days |
| At discontinuation | _ | _ |

At discontinuation: Performed within a possible window at a feasible time point.

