3.7.3.6 Columbia-Suicide Severity Rating Scale

(1) Time points

At screening, the initiation and Weeks 1, 2, 3, 4, 6, and 8 (or discontinuation) of the antidepressant treatment period (Phase A), Weeks 1, 2, 3, 4, 5, and 6 (or discontinuation) of the double-blind period (Phase B), post-treatment observation period, and Weeks 1, 2, 3, 4, 5, and 6 (or discontinuation) of the antidepressant-responder treatment-continuation period (Phase A+)

(2) Methods

This scale consists of the "Baseline Version," which assesses the lifetime history of suicide-related events and suicidal ideation and the "Since Last Visit Version," which focuses on suicidality since the last assessment in the trial. The "Baseline Version" will be used at screening and the "Since Last Visit Version" will be used at subsequent time points for C-SSRS assessment. The date, time, and results of assessment will be recorded in the source documents and the CRF.

The presence of suicidal ideation 1 or 2 will be assessed with "yes" or "no," and if the answer to 2 is "yes," suicidal ideation 3 to 5 will be assessed. If the answer to suicidal ideation 1 or 2 is "yes," the intensity of ideation will also be rated. Intensity of ideation will be rated on a 5-point scale for "frequency" and "duration" and a 6-point scale for "controllability," "deterrents," and "reasons for ideation." The following suicidal behavior will also be assessed with "yes" or "no," and the total numbers of each suicide attempt will be recorded. If there is an actual attempt, "actual lethality/physical damage" will be rated on a 6-point scale, and if actual lethality/physical injury is 0, "potential lethality" will be rated on a 3-point scale.

Suicidal ideation: 1. Wish to be dead 2. Non-specific active suicidal thoughts

- 3. Active suicidal ideation with any methods (not plan) without intent to act
- 4. Active suicidal ideation with some intent to act, without specific plan
- 5. Active suicidal ideation with specific plan and intent

Suicidal behavior: Actual attempt Non-suicidal self-injurious behavior Interrupted attempt Aborted attempt Preparatory acts or behavior Suicidal behavior Suicide (only for "Since Last Visit Version")

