7.6 Safety Analysis

Safety analysis for the double-blind period (Phase B) will be performed using the safety analysis set. Baseline is defined as Week 8 of the antidepressant treatment period (Phase A).

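### Does the missing item list for the C-SSRS suicidal behavior composite let non-suicidal self-injury distort the suicidality tables?

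*SAP*

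**What the plan says.** SAP 9.7.3 defines three related summaries. Suicidal behavior is Yes "for any item of suicidal behavior". Suicidality is Yes for any ideation or behavior item. Emergence of suicidal behavior is a change from No at baseline to Yes "after baseline for suicidal behavior". The same section also has the individual ideation and behavior items tabulated. It does not list the behavior items, and neither does Protocol 7.6.5.

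The only list is in Protocol 3.7.3.6, which describes data collection. It begins "The following suicidal behavior will also be assessed with" a yes or no answer and then gives seven entries: "Actual attempt Non-suicidal self-injurious behavior Interrupted attempt Aborted attempt Preparatory acts or behavior Suicidal behavior Suicide". The last of these is on the Since Last Visit form only.

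On the baseline, Protocol 7.6 states "Baseline is defined as Week 8 of the antidepressant treatment period". By Protocol 3.7.3.6 the lifetime form is used at screening, and the Since Last Visit form "will be used at subsequent time points for C-SSRS assessment".

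**The concern.** Two things look wrong on a first reading. First, a composite meant to capture suicidal acts appears, through the protocol's list, to include an act defined as non-suicidal. A lone self-injury would then inflate the suicidal behavior, suicidality and emergence counts. Second, emergence requires No at baseline. A subject whose only Yes at Week 8 was self-injury could not become emergent, even after an actual attempt in Phase B.

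Protocol 1.3 names suicidality among the important risks of the drug, so these outputs will be read closely. The counts may be small, and one reclassified subject could be visible. The tables that depend on the composites are CT-14.1 (suicidality) and CT-14.4 (treatment-emergent behavior and ideation), together with listing CT-14.6.

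**Working it through.** The plan states no figure to reproduce. The check applies the SAP rules to the possible item sets and then asks what is lost, and where.

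**1. Which readings are open?** SAP 9.7.3 speaks of any item and of summarizing the items, and CT-14.2 tabulates behavior by type. This describes a set of items. The composite therefore cannot be just the one protocol entry that is itself called suicidal behavior. The open question is whether non-suicidal self-injury belongs to the set.

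**2. What changes between the two readings?** Composite = Yes if any item in the set is Yes. Emergence = composite No at baseline and Yes afterwards.

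| Baseline | After baseline | All seven entries: behavior / emergence | Self-injury left out: behavior / emergence |
|---|---|---|---|
| none | self-injury only | Yes / Yes | No / No |
| self-injury only | actual attempt | Yes / No | Yes / Yes |
| none | actual attempt | Yes / Yes | Yes / Yes |
| self-injury only | self-injury only | Yes / No | No / No |

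The behavior columns refer to the period after baseline. In the second row the attempt is lost from emergence only. Behavior and suicidality do not require No at baseline, so both stay Yes.

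**3. How long is the baseline look-back?** Inputs are from Protocol Table 3.7.1.9-1, each with a window of plus or minus 2 days:

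- "Week 6 of the antidepressant treatment period (Phase A) | Day 43", so Day 41 to 45
- "Week 8 of the antidepressant treatment period (Phase A) | Day 57", so Day 55 to 59

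Shortest gap: 55 − 45 = 10 days. Longest: 59 − 41 = 18 days. Nominal: 57 − 43 = 14 days. Masking needs a self-injury within that interval as the only behavior item answered Yes.

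**4. Can such a subject be randomized?** The criteria for proceeding to Phase B use no C-SSRS item. Protocol 3.8.3.2 does require withdrawal for a Yes to C-SSRS question 4 or 5, a MADRS item 10 score of 5 or more, a HAM-D item 11 score of 3 or more, or a clinical judgment of high suicide risk. MADRS, HAM-D and C-SSRS are all rated at Week 8. These rules narrow the group but do not empty it.

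**5. Size.** With 240 per arm, one reclassified subject is 1/240 = 0.42 percentage points. In the overall brexpiprazole column it is 1/480 = 0.21 points. The first row of the table adds to the emergence count and the second subtracts from it, so the net direction is unknown.

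**6. Where would the event still be seen?** A self-injury would be in CT-14.2 and in listing PDATA-10.1.2. An attempt would be in the post-baseline behavior and suicidality counts, CT-14.2 and PDATA-10.1.3, a by-subject listing of actual attempts. SAP Appendix 4 has both suicide attempt and intentional self-harm among its suicidality terms, so an event reported as an adverse event under either term is also counted in CT-8.9.6.

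**The case for a change.** The case for a change is a fair one. The SAP fixes the item set for MADRS, HAM-D, MADRS-S, DIEPSS and AIMS in Section 3.5, and for DIEPSS it leaves the global severity item out of the total. The C-SSRS has no such entry. The only list available, taken literally, includes the self-injury item under the suicidal behavior heading, and neither document removes it. Two programmers could produce different counts from the same text. By-type tables let a reader detect a misclassified case, but they do not correct the composite.

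What stands is that the definition is incomplete and the literal reading can be made. What does not stand is that the literal reading is the likely one. The list tells sites what to record; it is not a scoring rule. It is also run together in the available text, so any layout that set the self-injury item apart from the others would be lost. An analyst asked for items of suicidal behavior has to override the word non-suicidal in the item's name in order to count it. It is also too strong to say that a later attempt would be hidden: only CT-14.4 and CT-14.6 would miss it.

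**Conclusion.** No change to the plan is needed. This is missing detail in the definition of descriptive safety summaries, and the item's plain label tells the analyst how to fill it. Misclassification arises only if the gap is filled against that label. Even then, one subject moves an arm by 0.42 percentage points (0.21 in the pooled column), and a masked attempt is missing from one count and one listing while remaining in several other planned outputs. No hypothesis test, error rate, sample size or efficacy endpoint is affected.

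This rests on three assumptions. Planned arm sizes of 240 are reached. The Phase B baseline is the Week 8 record, as Protocol 7.6 says and as the last-record rule in SAP 3.4 also gives. The 10 to 18 day look-back supposes on-window visits with no unscheduled C-SSRS between Weeks 6 and 8. No rate of self-injury is given, so the chance that any subject is affected cannot be calculated.

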- 3) Patients who have received at least 4 appropriate antidepressant drug treatments for the current major depressive episode but whose response was inadequate to all treatments
- 4) Patients receiving treatment with antipsychotics and psychostimulants for the current major depressive episode (excluding the use of sulpiride for depression/depressive state or gastric/duodenal ulcer)
- 5) Patients with a treatment history showing that all antidepressants (including those not used for the current major depressive episode) cannot be tolerated
- 6) Patients with a history of electroconvulsive therapy
- 7) Patients with a diagnosis of any of the following diseases according to DSM-5
 - a) Neurocognitive disorders
 - b) Schizophrenia spectrum and other psychotic disorders
 - c) Bipolar and related disorders
 - d) Feeding and eating disorders
 - e) Obsessive-compulsive disorder
 - f) Panic disorder
 - g) Posttraumatic stress disorder
- 8) Patients with a diagnosis of any personality disorders (borderline personality disorder, antisocial personality

- disorder, paranoid personality disorder, schizoid personality disorder, schizotypal personality disorder, and histrionic personality disorder) according to DSM-5
- 9) Patients experiencing hallucinations or delusions, or showing mood-incongruent psychotic features, in the current major depressive episode
- 10) Patients receiving a new psychotherapy within 6 weeks prior to informed consent
- 11) Patients who have previously taken brexpiprazole
- 12) Patients who have participated in other clinical trials within 60 days prior to informed consent
- 13) Patients with a HAM-D score for suicide (No. 11) of ≥ 3 at screening, those answering "Yes" to question 4 or 5 of Columbia-Suicide Severity Rating Scale (C-SSRS), or those who are, based on current psychiatric symptoms or past medical history, at high risk of suicide during the trial in the opinion of the investigator or subinvestigator
- 14) Patients with clinically significant neurological, hepatic, renal, metabolic, hematological, immunological, cardiovascular, pulmonary, or gastrointestinal disorders; patients can be enrolled if the conditions are mild or well controlled and will not hamper assessment of safety and efficacy.
- 15) Patients meeting any of the following criteria
- Patients with type 1 diabetes mellitus or patients with type 2 diabetes mellitus being treated with insulin

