3.8.3.2 Documenting Reasons for Discontinuation

All subjects have the right to withdraw and the investigator or subinvestigator can discontinue a subject's participation in the trial at any time if medically necessary. In addition, subjects meeting the following criteria must be withdrawn from the trial. Only

one reason for discontinuation (the main reason) can be recorded in the source documents and CRF, along with the date of discontinuation.

1) Adverse event:

- a) Death
- b) Subjects experiences exacerbation of symptoms of the underlying disease, and the investigator or subinvestigator judges that continued participation in the trial is inappropriate
- c) Subject experiences a change to the manic state
- d) Based on clinical symptoms, subject is considered to be at high risk of suicide in the opinion of the investigator or subinvestigator or has an MADRS score for Suicidal Thought (No. 10) of ≥ 5 or HAM-D suicide score (No. 11) of ≥ 3 , or those answering "Yes" to question 4 or 5 of C-SSRS.
- e) Subject decides to discontinue because of annoyance or discomfort due to a nonserious AE which is not otherwise determined to be an undue hazard
- f) Continuation of IMP would place the subject at undue risk as determined by the investigator or subinvestigator (eg, there is a safety concern possibly, probably, or likely related to IMP)
 - i) SAE
 - ii) Other safety concern or AE possibly, probably, or likely related to IMP
- 2) Subject's withdrawal of informed consent
 - a) Reasons unrelated to medical condition (issues regarding subject's convenience, such as a change of residence or other commitments: provide detail and review AE history with subject)
 - b) Withdrawal of informed consent (complete written withdrawal of consent form)
- 3) Marked noncompliance with the IMP regimen
 - a) Compliance rate of < 65% during the interval between 2 consecutive scheduled visits
- 4) Protocol deviation
 - a) Subject is discovered to have not been in accord with inclusion/exclusion criteria
 - b) Subject has received any prohibited concomitant drugs or therapies, or is judged to be in need of such
 - c) Dose of antidepressant (SSRI or SNRI) cannot be fixed from Week 7 of the antidepressant treatment period [Phase A])
- 5) Lost to follow-up
- 6) Pregnancy (see Section 5.5 Pregnancy)
- 7) Termination of all or part of the trial by the sponsor
- 8) Discontinuation of the trial site by the sponsor
- 9) Lack of efficacy

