CT-13.3	Summary of Mean Change From Baseline (End of Phase A) to Phase B by Study Week in BARS, Global Clinical Assessment of Akathisia (Safety Analysis Set)
CT-13.4	Summary of Mean Change From Baseline (End of Phase A) to Phase A+ by Study Week in DIEPSS (Phase A Plus Sample)
CT-13.5	Summary of Mean Change From Baseline (End of Phase A) to Phase A+ by Study Week in AIMS Total Score and Item Scores 8, 9 and 10 (Phase A Plus Sample)
CT-13.6	Summary of Mean Change From Baseline (End of Phase A) to Phase A+ by Study Week in BARS, Global Clinical Assessment of Akathisia (Phase A Plus Sample)
CT-14.1	C-SSRS During Phase B, Suicidality (Safety Analysis Set)
CT-14.2	C-SSRS During Phase B, Suicidal Behavior by Type (Safety Analysis Set)
CT-14.3	C-SSRS During Phase B, Suicidal Ideation by Type (Safety Analysis Set)
CT-14.4	C-SSRS During Phase B, Treatment Emergent Suicidal Behavior and Ideation (Safety Analysis Set)
CT-14.5	C-SSRS - Listing of Treatment-emergent Suicidal Ideation During Phase B (Safety Analysis Set)
CT-14.6	C-SSRS - Listing of Treatment-emergent Suicidal Behavior During Phase B (Safety Analysis Set)
CT-14.7	C-SSRS - Listing of Treatment-emergent Serious Ideation During Phase B (Safety Analysis Set)
CT-14.8	C-SSRS - Listing of Worsening Suicidal Ideation During Phase B (Safety Analysis Set)

CT-14.9	C-SSRS During Phase A, Suicidal Behavior by Type (ADT Sample)
CT-14.10	C-SSRS During Phase A, Suicidal Ideation by Type (ADT Sample)
CT-14.11	C-SSRS During Phase A+, Suicidal Behavior by Type (Phase A Plus Sample)
CT-14.12	C-SSRS During Phase A+, Suicidal Ideation by Type (Phase A Plus Sample)
PKT-1	Individual Subject and Summary of Brexpiprazole Plasma Concentrations Following 1 mg/day Doses of Brexpiprazole at Week 3 During Phase B (Pharmacokinetic Analysis Set)
PKT-2	Individual Subject and Summary of Brexpiprazole Plasma Concentrations Following 2 mg/day Doses of Brexpiprazole at Week 3 During Phase B (Pharmacokinetic Analysis Set)
PKT-3	Summary of Brexpiprazole Plasma Concentrations for Each CYP2D6 Phenotype Following 1 mg/day Doses of Brexpiprazole at Week 3 During Phase B (Pharmacokinetic Analysis Set)
PKT-4	Summary of Brexpiprazole Plasma Concentrations for Each CYP2D6 Phenotype Following 2 mg/day Doses of Brexpiprazole at Week 3 During Phase B (Pharmacokinetic Analysis Set)

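### The count of emergent serious suicidal ideation in SAP 9.7.3 leaves out subjects who go from grade 1-3 ideation at baseline to grade 4 or 5

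*SAP*

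**What the plan says.** SAP 9.7.3 and Protocol 7.6.5 list eight C-SSRS outcomes for Phase B, to be tabulated by treatment group. Four of the SAP definitions matter here:

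- "Emergence of serious suicidal ideation: Change from “No” at baseline to “Yes” with Grade 4 or 5 after baseline for suicidal ideation"
- "Emergence of suicidal ideation: Change from “No” at baseline to “Yes” after baseline for suicidal ideation"
- "Worsening of suicidal ideation: Increase in the grade of suicidal ideation from baseline"
- "Suicidality: “Yes” for any item of suicidal ideation or suicidal behavior"

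The section adds a breakdown by item: "Items of suicidal ideation and suicidal behavior will also be summarized in the same manner". SAP Appendix 5 plans table CT-14.3 (ideation by type), table CT-14.4 (treatment-emergent behaviour and ideation), listing CT-14.7 (treatment-emergent serious ideation) and listing CT-14.8 (worsening).

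Protocol 7.6 sets the Phase B safety baseline at Week 8 of Phase A. Protocol 3.7.3.6 grades ideation from 1 to 5 and uses the version covering the time since the last visit at every assessment after screening.

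On who can be in Phase B, exclusion criteria 13 and 29 and withdrawal criterion 1(d) in Protocol 3.8.3.2 name a yes "to question 4 or 5 of C-SSRS". They also act on a HAM-D item 11 score of 3 or more and on the investigator's judgement of high risk. The withdrawal criterion adds a MADRS item 10 score of 5 or more. None of them bars C-SSRS grade 1, 2 or 3 as such.

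**The concern.** The threshold for serious is grade 4 or 5, but the baseline condition is set at a different level, namely no ideation of any grade. A subject who enters Phase B at grade 3 and reaches grade 5 has newly serious ideation in the ordinary sense, yet does not count as an emergent serious case.

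Protocol 1.3 names suicidality as an important risk. Someone looking for new grade 4 or 5 ideation by treatment group would go to the row and listing that carry that name. If those can be too low, the treatment groups are compared on an incomplete count. With rare events, even one or two omitted subjects could alter how the groups look beside each other.

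The definition also departs from the SAP's practice elsewhere. For potentially clinically significant laboratory values and prolactin (SAP 9.3) and for QTc (SAP 9.6, confirmed in SAP 14), a new abnormality means that the subject was below the threshold at baseline and crossed it after treatment. The SAP gives no reason for treating ideation differently.

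**Working it through.** The plan states no figure on this point, so there is none to reproduce. The check takes each possible move to grade 4 or 5 and asks which planned outcome counts it.

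**Meaning of a baseline 'No'.** The any-ideation definition uses the same baseline 'No' for the same variable, and the SAP's Suicidal ideation outcome is a yes to any ideation item. So 'No' means that every ideation item is negative, which is grade 0.

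**Moves.** Four baseline grades (0, 1, 2, 3) and two later grades (4, 5) give 4 × 2 = 8 moves from non-serious to serious ideation. For a subject whose later grade is 4 or 5:

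| Baseline grade | Emergent serious ideation, SAP text | Worsening | Suicidal ideation and Suicidality | Items 4 and 5 by type | Baseline 0-3, then 4 or 5 |
|---|---|---|---|---|---|
| 0 | counted | counted | counted | counted | counted |
| 1, 2 or 3 | not counted | counted | counted | counted | counted |
| 4 or 5 | not counted | only 4 to 5 | counted | counted | not counted |

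The SAP text takes in 1 × 2 = 2 of the 8 moves and omits 3 × 2 = 6. A rule based on grade 0-3 at baseline takes in all 8. It still leaves out subjects already at grade 4 or 5.

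**Whether another output supplies the missing number.**

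- Worsening contains all six omitted moves, but pools them with any other rise, such as grade 1 to 2.
- Suicidal ideation and Suicidality have no baseline condition and no grade threshold.
- CT-14.3 shows items 4 and 5 by type. As described, it has no baseline condition and no combined row. Protocol 3.7.3.6 asks items 3 to 5 only after a yes to item 2, so one subject can be positive on several items. If the rows count items, the number with 4 or 5 lies somewhere between the larger row and the sum of the two.

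**Comparison with QTc.** Under SAP 9.6, a subject at 440 msec at baseline and 490 msec later is newly above 480 msec. Under SAP 9.7.3, a subject at grade 3 and later at grade 5 is not newly serious.

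**Size.** The number of subjects affected depends on how many have grade 1-3 at baseline and on their risk of reaching grade 4 or 5. The documents give neither.

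**The case against.** The best defence is that nothing is hidden. Every omitted subject is in the Worsening count, in CT-14.3 by treatment group, in CT-14.8 and in the subject-level C-SSRS listing PDATA-10.1.1. A reader could separate a 3-to-5 change from a 1-to-2 change by hand. Moreover, a yes to question 4 or 5 requires withdrawal in Phase A as well, and failure to withdraw is a tracked deviation category (SAP 7.6). So few randomised subjects should be at grade 4 or 5 at baseline, and nearly every positive item 4 or 5 in CT-14.3 is a new case. The definition also runs parallel to the any-ideation one, may match other trials, and feeds only descriptive tables.

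Most of this stands, and it keeps the point small. It does not remove it. CT-14.3 comes close, but its rows may overlap. It can also show more cases than the count and listing named for serious emergence, with nothing in the SAP to explain the difference.

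Three stronger readings are tempting and are not supported:

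- A reader might infer that the trial's main suicidality count is deficient. Neither document ranks the eight outcomes, and the one called Suicidality includes these subjects. No shell for CT-14.4 is given, so its full content is unknown.
- A reader might expect the emergence count to agree with withdrawals for suicide risk. Withdrawal criterion 1(d) pools C-SSRS, MADRS, HAM-D and clinical judgement, so no C-SSRS count need match it.
- A reader might attach a percentage. If a share p has grade 1-3 at baseline and carries r times the risk of subjects with none, the omitted share of new cases is pr/(pr + 1 − p). With p = 0.10 and r = 1 this is 0.10/1.00 = 10%. With p = 0.40 and r = 5 it is 2.0/2.6 = 77%. Both inputs are assumptions, and the width of the result only reflects them.

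**Conclusion.** The point holds as a limited reporting gap. The count named for emergent serious ideation, and listing CT-14.7, omit six of the eight ways in which a subject can newly reach grade 4 or 5. No planned count gives the combined number. The direction is known: the count can be too low and cannot be too high. The amount cannot be computed from the documents.

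The conclusion rests on the literal reading of 'No' as no ideation of any grade, and on some subjects entering Phase B with grade 1-3, which the criteria allow but do not quantify. The data are collected and appear in other outputs, and the primary analysis is not touched. The correction is still worth making, because suicidality is an important risk and the SAP already uses the threshold-based rule for other safety variables.

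**What to change.** In SAP 9.7.3, define emergence of serious suicidal ideation as a highest ideation grade of 0 (none) to 3 at baseline, with grade 4 or 5 at any later assessment in the Phase B period that the section already uses. Apply this to the emergence-of-serious-ideation count and to listing CT-14.7. Keep the present count, restricted to subjects with no ideation at baseline, as a sub-row so that results remain comparable with other trials.

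The cost is one line of SAP text, one derivation and one extra row, with no new data. The reported count may be slightly higher than under the current definition. No efficacy analysis or clinical rule changes.
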